3.8 GENERAL CONSIDERATIONS

3.8.1 Timing of Analyses

- Recruitment period will be: 24 months

Statistical Analysis Plan
Drug Substance DURVALUMAB/TREMELIMUMAB
Study Number ESR 15-11561-DUNE
EudraCT Nº: 2016-002858-20
Version Number: 1.1 dated on 30/NOV/2017

- Research Agreement executed: July 2016
- Projected IRB/IEC approval: Nov 2016
- First Subject In: Dec 2016
- 50% Enrollment: Dec 2017
- Last Subject In (100% enrollment): Dec 2018
- Last Subject Last Visit: Dec 2019
- Clinical Study Report April 2020

End of study is defined as Last Subject Last Visit.

1 TABLES, LISTING FIGURES

1.1 STUDY POPULATION

1.1.1 Recruited patients (sites/investigators)

In this section, the number of recruited patients overall and by sites is listed.

Table 2 Recruited patients by Hospital

Hospital	n (%)
Hospital 1:	
Hospital 2:	
Hospital 3:	
Hospital 4:	
Hospital 5:	
Hospital 6:	
Hospital 7:	
Hospital 8:	
Hospital 9:	
Hospital 10:	
Hospital 11:	
Hospital 12:	
Hospital 13:	
Hospital 14:	
Hospital 15:	
Hospital 16:	
Hospital 17:	
Hospital 18:	
Hospital 19:	
Hospital 20:	
Total	

1.1.2 Analyzed patients

If any patient is excluded from the study, it is listed in the table below, along with the reason for exclusion.

Table 3 Recruited patients and Analysis sets

	n	% ¹

Recruited patients	100,0
Reason for exclusion	
- Reason1	
- Reason 2	
...	
Analysis Sets	
Full Analysis Set: All allocated patients. Patients that fulfil every inclusion criteria and none of the exclusion criteria, without any other reason for their exclusion	 Yes  No
Per Protocol Analysis Set: Patients who were allocated and received at least one dose of the assigned study drug and had no major protocol deviations. The subjects will complete both baseline and at least one post-baseline tumor assessments (week 12).	 Yes  No
Safety Analysis Set: Patients who were allocated and received at least one dose of the study drug and had at least one post-baseline safety evaluation (week 12). This will be the analysis set for all safety evaluations.	 Yes  No
Pharmacodynamic Analysis Set: Patients who have received at least one dose of study drug and have evaluable pharmacodynamic data.	 Yes  No

In the following table, those patients excluded from any of the analysis sets will be listed along with the reasons for exclusion.

Table 4 List of patients excluded from any of the analysis set

Number of patient	Cohort	Hospital	Analysis set	Reason for exclusion

The number of patients included and excluded from each hospital will be reported.

Table 5 Included/Excluded patients by Hospital

Hospital 1

Hospital 2

Hospital 3

Hospital 4

Hospital 5

Hospital 6

Hospital 7

Hospital 8

Hospital 9

Hospital 10

Hospital 11

Hospital 12

Hospital 13

Hospital 14

Hospital 15

Hospital 16

Hospital 17

Hospital 18

Hospital 19

Hospital 20

Total n (100.0)

In the following table, the number of allocated patients in each one of the 4 cohorts by hospital will be shown.

Table 6 Patients allocated in each cohort by hospital

	Cohort 1	Cohort 2	Cohort 3	Cohort 4	Total
Hospital	n (%)				
Hospital 1					n (100%)
Hospital 2					n (100%)
Hospital 3					n (100%)
Hospital 4					n (100%)
Hospital 5					n (100%)
Hospital 6					n (100%)
Hospital 7					n (100%)
Hospital 8					n (100%)
Hospital 9					n (100%)

Hospital 10	n (100%)
Hospital 11	n (100%)
Hospital 12	n (100%)
Hospital 13	n (100%)
Hospital 14	n (100%)
Hospital 15	n (100%)
Hospital 16	n (100%)
Hospital 17	n (100%)
Hospital 18	n (100%)
Hospital 19	n (100%)
Hospital 20	n (100%)
Total	n (100%)

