6.1.2 Procedures for handling subjects incorrectly enrolled

Patients incorrectly enrolled in the trial will be considered as protocol deviations. If investigator considerer that the patient is obtaining benefit of the investigational treatment, patients could continue on therapy. They will not be considered for the primary endpoint of the trial, neither for efficacy nor biomarker secondary and exploratory analyses. Patients incorrectly enrolled that continue on treatment can be assessed for safety profile endpoint.

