11. STATISTICAL METHODS AND SAMPLE SIZE DETERMINATION

11.1. Description of analysis sets

The statistical analyses described in this section will be performed as further outlined in the Statistical Analysis Plan, which will be included in the clinical study report for this protocol.

Analysis Sets

The analysis sets will be defined as follows:

- **Full Analysis Set** will include all allocated subjects. This will be primary analysis set for the efficacy endpoints.
- **Per Protocol Analysis Set** will include those subjects who were allocated and received at least one dose of the assigned study drug and had no major protocol deviations. The subjects will complete both baseline and at least one post-baseline tumor assessments (week 12).
- **Safety Analysis Set** will include all subjects who were allocated and received at least one dose of the study drug and had at least one post-baseline safety evaluation (week 12). This will be the analysis set for all safety evaluations.
- **Pharmacodynamic Analysis Set**: All the subjects who have received at least one dose of study drug and have evaluable pharmacodynamic data.

Demographic and other baseline characteristics

Demographic and other baseline characteristics will be summarized and listed. For continuous demographic/baseline variables including age, weight, and vital signs, results will be summarized and presented as n, number of not available data (NA), mean, standard deviation, median, and minimum and maximum values. For categorical variables such as race/ethnicity, the number and percentage of subjects will be used.

Prior and concomitant medications

Concomitant medications will be assigned an 11-digit code using the World Health Organization Drug Dictionary (WHO DD) drug codes. Concomitant medications will be further coded to the appropriate Anatomical-Therapeutic-Chemical (ATC) code indicating therapeutic classification. Prior and concomitant medications will be summarized and listed by drug and drug class.

Efficacy Analyses

All efficacy analyses will be based primarily on the Full Analysis Set and secondarily on the Per

Clinical Study Protocol
 Drug Substance DURVALUMAB/TREMELIMUMAB
 Study Number ESR 15-11561-61-DUNE
 EudraCT Nº: 2016-002858-20
 Edition Number: 5.0 dated on June 09th, 2021

Protocol Analysis Set.

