3.6 SAMPLE SIZE

Sample size has been calculated using one-sample Superiority test (function OneSampleProportion. (NIS) of the Trial Size package of R software). According to previous knowledge, it is estimated that the reference value for the likelihood to be progression-free at 9 months is 30% and we expect an increase of 20% with a superiority margin of 10%. With a unilateral alpha level of 5% and 80% power, we estimate to include 28 patients per group, with an expected lost to follow-up rate of 10%, a final sample size in each 1, 2 and 3 cohort will include 31 patients.

For cohort 4, and according to previous knowledge, it is estimated that the reference proportion of patients being alive at 9 months is 13% and we expect an increase of 10% with a superiority margin of 5%. With a unilateral alpha level of 5% and 80% power, we estimate to include 30 patients per group, with an expected lost to follow-up rate of 10%, a final sample size will include 33 patients.

Summarizing, total sample size will include 126 patients: 31 patients for cohorts 1 to 3, and 33 for cohort 4.

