3.7.3 Planned Method of Analysis

Summary tables (descriptive statistics and frequency tables) will be provided for all baseline variables, efficacy variables, and safety variables, as appropriate. Continuous variables will be summarized with descriptive statistics (mean, standard deviation, range, and median). Ninety-five (95) percent confidence intervals (95% CI) may also be presented, as appropriate. Frequency counts and percentage of subjects within each category will be provided for categorical data.

The primary efficacy analysis will be performed using the binomial test procedure. Missing data will be treated using statistical multiple random imputation.

Concordance between investigator assessment and independent central radiology review will be analyzed using Cohen's Kappa. Although no significant differences are expected, a sensitivity analysis for the primary efficacy analysis will be performed using as response variable independent central radiology assessment.

Secondary endpoints will be summarized with descriptive statistics. Continuous variables will be summarized with n, mean, standard deviation, and range, frequency counts and percentage of subjects within each category will be provided for categorical data. Multivariate regression models will be used to study relations between explanatory variables and primary endpoint. Survival analysis will be performed to analyze PFS, Kaplan-Meier curves will be presented and possible comparisons will be tested using the log-rank test or the Cox proportional hazard model for multivariate analysis, hazard ratios (HR) and their 95% confidence interval (CI95%) will be provided. Patients with lost of follow-up or treatment discontinuation will be included in the final analysis of primary endpoint if they have at least one tumor evaluation and considered as censored data for survival endpoints.

R software version 3.2.1 will be used for all analysis.

Safety Analyses

Safety analyses will be based on the Safety Analysis Set. All safety analyses will be summarized separately by cohort. Adverse events and serious adverse events, laboratory test results, physical examination findings and vital signs, and their changes from baseline will be summarized using descriptive statistics. Abnormal values will be flagged.

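### The primary efficacy set is defined as all allocated patients, but other clauses remove some of them and nothing says which rule prevails

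*SAP*

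**What the plan says.** Four rules bear on who counts in the primary analysis.

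- **All allocated.** Protocol 11.1 says the Full Analysis Set "will include all allocated subjects. This will be primary analysis set for the efficacy endpoints". SAP 3.7.1 says the same.
- **Eligible only.** SAP Table 3, in section 1.1.2, opens its Full Analysis Set cell with all allocated patients. The same cell then restricts the set to "Patients that fulfil every inclusion criteria and none of the exclusion criteria, without any other reason for their exclusion". The final clause is not defined anywhere.
- **Incorrectly enrolled patients out.** Protocol 6.1.2 and SAP 3.3.4 treat them as protocol deviations and state: "They will not be considered for the primary endpoint of the trial, neither for efficacy nor biomarker secondary and exploratory analyses".
- **Tumour evaluation needed.** SAP 3.7.3 and Protocol 11.2 say that patients lost to follow-up or off treatment "will be included in the final analysis of primary endpoint if they have at least one tumor evaluation".

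On the test itself, SAP 3.7.3 says: "The primary efficacy analysis will be performed using the binomial test procedure". It is done separately for each cohort.

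**The concern.** A patient who was allocated and later found ineligible is inside the primary denominator under the first rule and outside it under the second and third. A patient who stops or is lost before any on-treatment scan is inside under the first and, read literally, outside under the fourth. Table 3 disagrees with itself within one cell.

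The documents do not say which rule governs, who decides that a patient was incorrectly enrolled, or that the decision comes before outcomes are known. This matters more than usual here. The trial is open label, and clinical benefit at 9 months rests on investigator assessment. Protocol 6.1.2 also lets the investigator keep an incorrectly enrolled patient on therapy if the patient seems to be benefiting, so benefit may already be under discussion when status is handled. The eligibility test is not uniform either. For cohort 1 the mitotic limit is 20 in SAP 3.3.2 and 10 in Protocol 4.1, so Table 3 could classify the same patient differently depending on which list is applied.

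At stake is whether the same data yield one primary result per cohort or two.

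**Working it through.** **Inputs (SAP 3.6, same in Protocol 11.3).** For cohorts 1 to 3 the reference rate is 30%, the planned gain 20 points and the margin 10 points. For cohort 4 the reference is 13%, the planned gain 10 points and the margin 5 points. Alpha is one-sided 5%. Enrolled N is 31 in each of cohorts 1 to 3 and 33 in cohort 4.

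**The plan's own figures.** The dropout step reproduces: 28 × 1.10 = 30.8, rounded up to 31, and 30 × 1.10 = 33. The starting figures do not. For cohorts 1 to 3, (1.645 + 0.842)² × p(1−p) / (0.20 − 0.10)² gives about 130 at p = 0.30 and 155 at p = 0.50, against the stated 28. That is a separate problem. The check below uses only the enrolled N, the reference rates and the one-sided 5%.

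**Formula.** The exact one-sided p-value is P(X ≥ x), with X binomial (n, p0). A success is a patient with clinical benefit at 9 months (cohorts 1 to 3) or alive at 9 months (cohort 4). The documents do not say whether the tested null is the reference rate or the reference plus margin, so both are shown.

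**Effect of excluding one failure.**

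| Cohort | Null p0 | All allocated | One failure excluded |
|---|---|---|---|
| 1 to 3 | 30% | 14/31, p=0.0534 | 14/30, p=0.0401 |
| 1 to 3 | 40% | 17/31, p=0.0677 | 17/30, p=0.0481 |
| 4 | 13% | 8/33, p=0.0567 | 8/32, p=0.0482 |
| 4 | 18% | 10/33, p=0.0598 | 10/32, p=0.0494 |

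All four go from fail to pass. With nobody excluded, the smallest passing counts are 15/31, 18/31, 9/33 and 11/33. One exclusion lowers each by one.

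**Other direction.** Excluding one success does not overturn a pass at one-sided 5%: 15/31 (p=0.0239) becomes 14/30 (p=0.0401), and 9/33 (p=0.0218) becomes 8/32 (p=0.0482). Excluding two does: 13/29 gives p=0.0652 and 7/31 gives p=0.0990. A single exclusion therefore flips only towards success.

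**How likely is the boundary count?** At the planned rates:

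- Cohorts 1 to 3 (50%): P(X = 14 of 31) = 0.123. P(X = 17 of 31) is the same by symmetry.
- Cohort 4 (23%): P(X = 8 of 33) = 0.158, and P(X = 10 of 33) = 0.094.
- At least one of the four cohorts, reference-rate nulls, cohorts independent: 1 − (1 − 0.1235)³ × (1 − 0.158) = 0.43.

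**Adding the need for an excludable failure.** The documents give no ineligibility rate. Assume 2% to 10%, unrelated to outcome, and ignore ineligible successes:

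- Cohorts 1 to 3 (17 failures at 14/31): 0.1235 × (1 − 0.98¹⁷) = 0.036, up to 0.1235 × (1 − 0.90¹⁷) = 0.103.
- Cohort 4 (25 failures at 8/33): 0.158 × (1 − 0.98²⁵) = 0.063, up to 0.158 × (1 − 0.90²⁵) = 0.147.

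**The case against.** The best defence is that a specific rule qualifies a general one. Protocol 6.1.2 and SAP 3.3.4 agree with each other and with the second half of the Table 3 cell, so the natural reading would be all allocated patients except those incorrectly enrolled. That reading is plausible, but no passage adopts it. If it is intended, the definitions in Protocol 11.1 and SAP 3.7.1 are wrong as written, so a correction is needed either way.

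Safeguards exist. Eligibility is confirmed before dosing, Protocol section 4 allows no exceptions, SAP Table 4 lists every exclusion with its reason, and a per-protocol analysis is already planned. These make exclusions visible. They do not settle which result is primary.

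The plan states no explicit success criterion, and SAP Tables 92 and 93 report 95% intervals rather than p-values. On exact 95% intervals the main examples do not change: 14/31 gives 27.3% to 64.0% and 14/30 gives 28.3% to 65.7%, both covering 30%. 8/33 gives 11.1% to 42.3% and 8/32 gives 11.5% to 43.4%, both covering 13%. This stands as a limit on those counts. The sensitivity then moves to other counts: 15/31 and 9/33 exclude the reference rate, while 14/30 and 8/32, each with one success removed, do not.

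Finally, these are single-arm exploratory cohorts with no randomisation to protect, so excluding baseline eligibility failures is defensible if it is decided without knowledge of outcome. That is fair. All allocated is preferred here because both documents already name it as primary.

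A reader might infer that outcomes will be known before the set is fixed, or that any single exclusion would change the result. The documents support neither. They are silent on timing, and the flip occurs only at a boundary count.

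**Conclusion.** The primary denominator is contradictory as written in all four cohorts, and the plan must be corrected. The sections on analysis sets, incorrect enrolment and the method of analysis, together with the Table 3 shell, cannot all be followed for an allocated but ineligible patient, or for one lost or discontinued without a tumour evaluation.

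The numerical consequence is real but conditional. One excluded failure turns a fail into a pass at exactly one count per cohort and null. The chance of that count at the planned rates is about 12% per cohort in cohorts 1 to 3 and 16% in cohort 4 against the reference rates. An excludable failure is also required, and its frequency is unknown. These figures assume an exact one-sided 5% binomial test at the full enrolled N. The conclusion that the text needs repair does not depend on them.

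**What to change.** 1. Keep one primary set: all allocated patients, including any later found ineligible.
2. In SAP Table 3, delete the eligibility condition and the open-ended final clause from the Full Analysis Set cell.
3. Amend Protocol 6.1.2 and SAP 3.3.4 so that incorrectly enrolled patients leave only the per-protocol set. Add a sensitivity analysis of the primary endpoint without them.
4. Remove the tumour-evaluation condition from the primary analysis in Protocol 11.2 and SAP 3.7.3, or reconcile it with the all-allocated set. The planned multiple imputation already offers a route for missing clinical benefit. SAP 3.7.5 does not spell this out for 9-month survival, so state the rule for cohort 4.
5. Name who classifies deviations, and require the classifications to be fixed before outcome review.
6. State the null and the passing count for each cohort at its actual N.

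The cost is a protocol and SAP amendment. Because it changes the primary analysis population, it probably needs submission to the health authorities and the ethics committee under Protocol 12.4. No new data are needed.

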1.2 DEMOGRAPHIC AND CLINICAL BASELINE CHARACTERISTICS

For the descriptive analysis of the patients, the full analysis set is used (see section 29).

Table 7 Sociodemographic characteristics in overall

	n	Mean (SD)	Median (IQR)	Min-Max	95% CI of the mean
Age (years)					
	n			% ¹	95% CI of the proportion
Gender					
Male					
Female					
UNK					
Race/ethnicity					
Caucasic					
Afro-american					
Others					
UNK					

¹ Calculated percentage from the total of patients with available data

Table 8 Vital signs in overall

	n	Mean (SD)	Median (IQR)	Min-Max	95% CI of the mean
Weight (kg)					
Height (cm)					

BMI

Temperature

Respiratory rate

Systolic blood pressure

Diastolic blood pressure

Table 9 ECOG in overall

	n	%¹	95% CI of the proportion
ECOG			
0			
1			
2			
3			
4			
UNK			

¹ Calculated percentage from the total of patients with available data

Table 10 Tumor characteristics overall

	n	%¹	95% CI of the proportion
Histological type			
Well differentiated			
Moderately differentiated			
Poorly differentiated			
Ki-67 Index			
≤2			
3-20			
>20			
Mitotic Index 10 CGA			
GEP-NETs			
<2			
2-20			
>20			
Lung/thymus			
<2			
2-10			

>10

Octreoscan/PET

Positive

Negative

Number of extranodal locations

0

1

2

3 or more

UNK

¹ Calculated percentage from the total of patients with available data

Table 11 Time since radiological progression to inclusion

	n	Mean (SD)	Median (IQR)	Min-Max	95% CI of the mean
Time since radiological PE to inclusion					

Table 12 Previous antineoplastic therapy

Name	n	%¹	95% CI of the proportion
Therapy 1			
Therapy 2			
Therapy 3			
Therapy 4			
Therapy 5			
Therapy 6			

¹ Calculated percentage from the total of patients with available data

Table 13 Best response to previous antineoplastic therapy

	n	%¹	95% CI of the proportion
Complete response			
Partial response			
Stable Disease			
Progression			
UNK			
Total			

¹ Calculated percentage from the total of patients with available data

Table 14 Baseline hematology laboratory test in overall

	n	Mean (SD)	Median (IQR)	Min-Max	95% CI of the mean
Basophils					
Eosinophils					
Hematocrit					
Hemoglobin					
Lymphocytes					
Mean corpuscular hemoglobin					
Mean corpuscular hemoglobin concentration					
Mean corpuscular volume					
Monocytes					
Neutrophils					
Platelet count					
Red blood cell count					
Total white cell count					

Table 15 Baseline clinical chemistry (serum or plasma) laboratory test in overall

	n	Mean (SD)	Median (IQR)	Min-Max	95% CI of the mean
Albumin					
Alkaline phosphatase					
Alanine aminotransferase					
Amylase					
Aspartate aminotransferase					
Bicarbonate					
Calcium					
Chloride					
Creatinine					
Clearance creatinine					
Gamma glutamyltransferase					

Glucose

Lactate dehydrogenase

Lipase

Magnesium

Potassium

Sodium

Total bilirubin

Total protein

Urea or blood urea nitrogen, depending on local practice

Uric acid

Table 16 Baseline urinalysis test in overall

	n	Mean (SD)	Median (IQR)	Min-Max	95% CI of the mean
Bilirubin					
Blood					
Glucose					
Ketones					
pH					
Protein					
Specific gravity					
Colour and appearance					

Table 17 Baseline TSH, fT3 and fT4 in overall

	n	Mean (SD)	Median (IQR)	Min-Max	95% CI of the mean
TSH					
fT3					
fT4					

Table 18 Baseline coagulation in overall

	n	Mean (SD)	Median (IQR)	Min-Max	95% CI of the mean

**Partial thromboplastin Time
 (PTT)**

Prothrombin Time (PT)

**International Normalized
 Ratio (INR)**

	n	% ¹	95% CI of the proportion
Anti PNS			
Positive			
Negative			
UNK			

¹ Calculated percentage from the total of patients with available data

Table 19 Hepatitis and HIV serologies in overall

	n	% ¹	95% CI of the proportion
Hepatitis HCV			
Positive			
Negative			
HBsAg			
Positive			
Negative			
HBcAg			
Positive			
Negative			
HIV			
Positive			
Negative			

¹ Calculated percentage from the total of patients with available data

Table 20 Disease-specific tumor markers and Anti PNS

	n	Mean (SD)	Median (IQR)	Min-Max	95% CI of the mean
Cg A					
Neuron specific enolase					

Concomitant medications will be coded to the appropriate Anatomical-Therapeutic-Chemical (ATC) code indicating therapeutic classification. Prior and concomitant medications will be summarized and listed by drug and drug class.

Table 21 Concomitant medication

Concomitant medication Drug	n	% ¹
Drug class 1		
Drug 1.1		
Drug 1.2		
Drug 1....		
Drug class 2		
Drug 2.1		
Drug 2.2		
Drug 2....		
Drug class 3		
Drug 3.1		
Drug 3.2		
Drug 3....		

¹ Calculated percentage from the total of patients with available data

1.2.1 Demographic and other baseline characteristics in cohort 1

For the descriptive analysis of the patients, the full analysis set is used (see section 29).

Table 22 Sociodemographic characteristics in overall in cohort 1

	n	Mean (SD)	Median (IQR)	Min-Max	95% CI of the mean
Age (years)					
	n			% ¹	95% CI of the proportion
Gender					
Male					
Female					
UNK					
Race/ethnicity					
Caucasic					
Afro-american					
Others					
UNK					

¹ Calculated percentage from the total of patients with available data

Table 23 Vital signs in overall in cohort 1

	n	Mean (SD)	Median (IQR)	Min-Max	95% CI of the mean
Weight (kg)					

Height (cm)

BMI

Temperature

Respiratory rate

Systolic blood pressure

Diastolic blood pressure

Table 24 ECOG in overall in cohort 1

	n	%¹	95% CI of the proportion
ECOG			
0			
1			
2			
3			
4			
UNK			

¹ Calculated percentage from the total of patients with available data

Table 25 Tumor characteristics overall in cohort 1

	n	%¹	95% CI of the proportion
Histological type			
Well differentiated			
Moderately differentiated			
Poorly differentiated			
Ki-67 Index			
≤2			
3-20			
>20			
Mitotic Index 10 CGA			
GEP-NETs			
<2			
2-20			
>20			
Lung/thymus			
<2			

2-10

>10

Octreoscan/PET

Positive

Negative

Number of extranodal
 locations

0

1

2

3 or more

UNK

¹ Calculated percentage from the total of patients with available data

Table 26 Time since radiological progression to inclusion in cohort 1

	n	Mean (SD)	Median (IQR)	Min-Max	95% CI of the mean
Time since radiological PE to inclusion					

Table 27 Previous antineoplastic therapy in cohort 1

Name	n	% ¹	95% CI of the proportion
Therapy 1			
Therapy 2			
Therapy 3			
Therapy 4			
Therapy 5			
Therapy 6			

¹ Calculated percentage from the total of patients with available data

Table 28 Best response to previous antineoplastic therapy in cohort 1

	n	% ¹	95% CI of the proportion
Complete response			
Partial response			
Stable Disease			
Progression			
UNK			

Total

¹ Calculated percentage from the total of patients with available data

Table 29 Baseline hematology laboratory test in overall in cohort 1

	n	Mean (SD)	Median (IQR)	Min-Max	95% CI of the mean
Basophils					
Eosinphils					
Hematocrit					
Hemoglobin					
Lymphocytes					
Mean corpuscular hemoglobin					
Mean corpuscular hemoglobin concentration					
Mean corpuscular volume					
Monocytes					
Neutrophils					
Platelet count					
Red blood cell count					
Total white cell count					

Table 30 Baseline clinical chemistry (serum or plasma) laboratory test in overall in cohort 1

	n	Mean (SD)	Median (IQR)	Min-Max	95% CI of the mean
Albumin					
Alkaline phosphatase					
Alanine aminotransferase					
Amylase					
Aspartate aminotransferase					
Bicarbonate					
Calcium					
Chloride					
Creatinine					
Clearance creatinine					

Gamma glutamyltransferase

Glucose

Lactate dehydrogenase

Lipase

Magnesium

Potassium

Sodium

Total bilirubin

Total protein

Urea or blood urea nitrogen, depending on local practice

Uric acid

Table 31 Baseline urinalysis test in overall in cohort 1

	n	Mean (SD)	Median (IQR)	Min-Max	95% CI of the mean
Bilirubin					
Blood					
Glucose					
Ketones					
pH					
Protein					
Specific gravity					
Colour and appearance					

Table 32 Baseline TSH, fT3 and fT4 in overall in cohort 1

	n	Mean (SD)	Median (IQR)	Min-Max	95% CI of the mean
TSH					
fT3					
fT4					

Table 33 Baseline coagulation in overall in cohort 1

	n	Mean (SD)	Median (IQR)	Min-Max	95% CI of the mean

**Partial thromboplastin Time
 (PTT)**

Prothrombin Time (PT)

**International Normalized
 Ratio (INR)**

	n	% ¹	95% CI of the proportion
Anti PNS			
Positive			
Negative			
UNK			

¹ Calculated percentage from the total of patients with available data

Table 34 Hepatitis and HIV serologies in overall in cohort 1

	n	% ¹	95% CI of the proportion
Hepatitis HCV			
Positive			
Negative			
HBsAg			
Positive			
Negative			
HBcAg			
Positive			
Negative			
HIV			
Positive			
Negative			

¹ Calculated percentage from the total of patients with available data

Table 35 Disease-specific tumor markers and Anti PNS in cohort 1

	n	Mean (SD)	Median (IQR)	Min-Max	95% CI of the mean
Cg A					
Neuron specific enolase					

Concomitant medications will be coded to the appropriate Anatomical-Therapeutic-Chemical (ATC) code indicating therapeutic classification. Prior and concomitant medications will be summarized and listed by drug and drug class.

Table 36 Concomitant medication in cohort 1

Concomitant medication Drug	n	% ¹
Drug class 1		
Drug 1.1		
Drug 1.2		
Drug 1....		
Drug class 2		
Drug 2.1		
Drug 2.2		
Drug 2....		
Drug class 3		
Drug 3.1		
Drug 3.2		
Drug 3....		

¹ Calculated percentage from the total of patients with available data

1.2.2 Demographic and other baseline characteristics in cohort 2

For the descriptive analysis of the patients, the full analysis set is used (see section 29).

Table 37 Sociodemographic characteristics in overall in cohort 2

	n	Mean (SD)	Median (IQR)	Min-Max	95% CI of the mean
Age (years)					
	n			% ¹	95% CI of the proportion
Gender					
Male					
Female					
UNK					
Race/ethnicity					
Caucasic					
Afro-american					
Others					
UNK					

¹ Calculated percentage from the total of patients with available data

Table 38 Vital signs in overall in cohort 2

	n	Mean (SD)	Median (IQR)	Min-Max	95% CI of the mean
Weight (kg)					

Height (cm)

BMI

Temperature

Respiratory rate

Systolic blood pressure

Diastolic blood pressure

Table 39 ECOG in overall in cohort 2

	n	%¹	95% CI of the proportion
ECOG			
0			
1			
2			
3			
4			
UNK			

¹ Calculated percentage from the total of patients with available data

Table 40 Tumor characteristics overall in cohort 2

	n	%¹	95% CI of the proportion
Histological type			
Well differentiated			
Moderately differentiated			
Poorly differentiated			
Ki-67 Index			
≤2			
3-20			
>20			
Mitotic Index 10 CGA			
GEP-NETs			
<2			
2-20			
>20			
Lung/thymus			
<2			

2-10

>10

Octreoscan/PET

Positive

Negative

**Number of extranodal
locations**

0

1

2

3 or more

UNK

¹ Calculated percentage from the total of patients with available data

Table 41 Time since radiological progression to inclusion in cohort 2

	n	Mean (SD)	Median (IQR)	Min-Max	95% CI of the mean
Time since radiological PE to inclusion					

Table 42 Previous antineoplastic therapy in cohort 2

Name	n	%¹	95% CI of the proportion
Therapy 1			
Therapy 2			
Therapy 3			
Therapy 4			
Therapy 5			
Therapy 6			

¹ Calculated percentage from the total of patients with available data

Table 43 Best response to previous antineoplastic therapy in cohort 2

	n	%¹	95% CI of the proportion
Complete response			
Partial response			
Stable Disease			
Progression			
UNK			
Total			

¹ Calculated percentage from the total of patients with available data

Table 44 Baseline hematology laboratory test in overall in cohort 2

	n	Mean (SD)	Median (IQR)	Min-Max	95% CI of the mean
Basophils					
Eosinophils					
Hematocrit					
Hemoglobin					
Lymphocytes					
Mean corpuscular hemoglobin					
Mean corpuscular hemoglobin concentration					
Mean corpuscular volume					
Monocytes					
Neutrophils					
Platelet count					
Red blood cell count					
Total white cell count					

Table 45 Baseline clinical chemistry (serum or plasma) laboratory test in overall in cohort 2

	n	Mean (SD)	Median (IQR)	Min-Max	95% CI of the mean
Albumin					
Alkaline phosphatase					
Alanine aminotransferase					
Amylase					
Aspartate aminotransferase					
Bicarbonate					
Calcium					
Chloride					
Creatinine					
Clearance creatinine					
Gamma					

glutamyltransferase

Glucose

Lactate dehydrogenase

Lipase

Magnesium

Potassium

Sodium

Total bilirubin

Total protein

Urea or blood urea nitrogen, depending on local practice

Uric acid

Table 46 Baseline urinalysis test in overall in cohort 2

	n	Mean (SD)	Median (IQR)	Min-Max	95% CI of the mean
Bilirubin					
Blood					
Glucose					
Ketones					
pH					
Protein					
Specific gravity					
Colour and appearance					

Table 47 Baseline TSH, fT3 and fT4 in overall in cohort 2

	n	Mean (SD)	Median (IQR)	Min-Max	95% CI of the mean
TSH					
fT3					
fT4					

Table 48 Baseline coagulation in overall in cohort 2

	n	Mean (SD)	Median (IQR)	Min-Max	95% CI of the mean

**Partial thromboplastin Time
 (PTT)**

Prothrombin Time (PT)

**International Normalized
 Ratio (INR)**

	n	% ¹	95% CI of the proportion
Anti PNS			
Positive			
Negative			
UNK			

¹ Calculated percentage from the total of patients with available data

Table 49 Hepatitis and HIV serologies in overall in cohort 2

	n	% ¹	95% CI of the proportion
Hepatitis HCV			
Positive			
Negative			
HBsAg			
Positive			
Negative			
HBcAg			
Positive			
Negative			
HIV			
Positive			
Negative			

¹ Calculated percentage from the total of patients with available data

Table 50 Disease-specific tumor markers and Anti PNS in cohort 2

	n	Mean (SD)	Median (IQR)	Min-Max	95% CI of the mean
Cg A					
Neuron specific enolase					

Concomitant medications will be coded to the appropriate Anatomical-Therapeutic-Chemical (ATC) code indicating therapeutic classification. Prior and concomitant medications will be summarized and listed by drug and drug class.

Table 51 Concomitant medication in cohort 2

Concomitant medication Drug	n	% ¹
Drug class 1		
Drug 1.1		
Drug 1.2		
Drug 1....		
Drug class 2		
Drug 2.1		
Drug 2.2		
Drug 2....		
Drug class 3		
Drug 3.1		
Drug 3.2		
Drug 3....		

¹ Calculated percentage from the total of patients with available data

1.2.3 Demographic and other baseline characteristics in cohort 3

For the descriptive analysis of the patients, the full analysis set is used (see section 29).

Table 52 Sociodemographic characteristics in overall in cohort 3

	n	Mean (SD)	Median (IQR)	Min-Max	95% CI of the mean
Age (years)					
	n			% ¹	95% CI of the proportion
Gender					
Male					
Female					
UNK					
Race/ethnicity					
Caucasic					
Afro-american					
Others					
UNK					

¹ Calculated percentage from the total of patients with available data

Table 53 Vital signs in overall in cohort 3

	n	Mean (SD)	Median (IQR)	Min-Max	95% CI of the mean
Weight (kg)					
	n			% ¹	95% CI of the proportion

Height (cm)

BMI

Temperature

Respiratory rate

Systolic blood pressure

Diastolic blood pressure

Table 54 ECOG in overall in cohort 3

	n	%¹	95% CI of the proportion
ECOG			
0			
1			
2			
3			
4			
UNK			

¹ Calculated percentage from the total of patients with available data

Table 55 Tumor characteristics overall in cohort 3

	n	%¹	95% CI of the proportion
Histological type			
Well differentiated			
Moderately differentiated			
Poorly differentiated			
Ki-67 Index			
≤2			
3-20			
>20			
Mitotic Index 10 CGA			
GEP-NETs			
<2			
2-20			
>20			
Lung/thymus			
<2			

2-10
>10
Octreoscan/PET
Positive
Negative
Number or extranodal locations
0
1
2
3 or more
UNK

¹ Calculated percentage from the total of patients with available data

Table 56 Time since radiological progression to inclusion in cohort 3

	n	Mean (SD)	Median (IQR)	Min-Max	95% CI of the mean
Time since radiological PE to inclusion					

Table 57 Previous antineoplastic therapy in cohort 3

Name	n	%¹	95% CI of the proportion
Therapy 1			
Therapy 2			
Therapy 3			
Therapy 4			
Therapy 5			
Therapy 6			

¹ Calculated percentage from the total of patients with available data

Table 58 Best response to previous antineoplastic therapy in cohort 3

	n	%1	95% CI of the proportion
Complete response			
Partial response			
Stable Disease			
Progression			
UNK			
Total			

¹ Calculated percentage from the total of patients with available data

Table 59 Baseline hematology laboratory test in overall in cohort 3

	n	Mean (SD)	Median (IQR)	Min-Max	95% CI of the mean
Basophils					
Eosinophils					
Hematocrit					
Hemoglobin					
Lymphocytes					
Mean corpuscular hemoglobin					
Mean corpuscular hemoglobin concentration					
Mean corpuscular volume					
Monocytes					
Neutrophils					
Platelet count					
Red blood cell count					
Total white cell count					

Table 60 Baseline clinical chemistry (serum or plasma) laboratory test in overall in cohort 3

	n	Mean (SD)	Median (IQR)	Min-Max	95% CI of the mean
Albumin					
Alkaline phosphatase					
Alanine aminotransferase					
Amylase					
Aspartate aminotransferase					
Bicarbonate					
Calcium					
Chloride					
Creatinine					
Clearance creatinine					
Gamma glutamyltransferase					
Glucose					

Lactate dehydrogenase

Lipase

Magnesium

Potassium

Sodium

Total bilirubin

Total protein

Urea or blood urea nitrogen, depending on local practice

Uric acid

Table 61 Baseline urinalysis test in overall in cohort 3

	n	Mean (SD)	Median (IQR)	Min-Max	95% CI of the mean
Bilirubin					
Blood					
Glucose					
Ketones					
pH					
Protein					
Specific gravity					
Colour and appearance					

Table 62 Baseline TSH, fT3 and fT4 in overall in cohort 3

	n	Mean (SD)	Median (IQR)	Min-Max	95% CI of the mean
TSH					
fT3					
fT4					

Table 63 Baseline coagulation in overall in cohort 3

	n	Mean (SD)	Median (IQR)	Min-Max	95% CI of the mean
Partial thromboplastin Time (PTT)					
Prothrombin Time (PT)					

**International Normalized
 Ratio (INR)**

	n	% ¹	95% CI of the proportion
Anti PNS			
Positive			
Negative			
UNK			

¹ Calculated percentage from the total of patients with available data

Table 64 Hepatitis and HIV serologies in overall in cohort 3

	n	% ¹	95% CI of the proportion
Hepatitis HCV			
Positive			
Negative			
HBsAg			
Positive			
Negative			
HBcAg			
Positive			
Negative			
HIV			
Positive			
Negative			

¹ Calculated percentage from the total of patients with available data

Table 65 Disease-specific tumor markers and Anti PNS in cohort 3

	n	Mean (SD)	Median (IQR)	Min-Max	95% CI of the mean
Cg A					
Neuron specific enolase					

Concomitant medications will be coded to the appropriate Anatomical-Therapeutic-Chemical (ATC) code indicating therapeutic classification. Prior and concomitant medications will be summarized and listed by drug and drug class.

Table 66 Concomitant medication in cohort 3

Concomitant medication Drug	n	% ¹

Drug class 1

Drug 1.1

Drug 1.2

Drug 1....

Drug class 2

Drug 2.1

Drug 2.2

Drug 2....

Drug class 3

Drug 3.1

Drug 3.2

Drug 3....

¹ Calculated percentage from the total of patients with available data

1.2.4 Demographic and other baseline characteristics in cohort 4

For the descriptive analysis of the patients, the full analysis set is used (see section 29).

Table 67 Sociodemographic characteristics in overall in cohort 4

	n	Mean (SD)	Median (IQR)	Min-Max	95% CI of the mean
Age (years)					
	n			% ¹	95% CI of the proportion
Gender					
Male					
Female					
UNK					
Race/ethnicity					
Caucasic					
Afro-american					
Others					
UNK					

¹ Calculated percentage from the total of patients with available data

Table 68 Vital signs in overall in cohort 4

	n	Mean (SD)	Median (IQR)	Min-Max	95% CI of the mean
Weight (kg)					
Height (cm)					

BMI

Temperature

Respiratory rate

**Systolic blood
pressure**

**Diastolic blood
pressure**

Table 69 ECOG in overall in cohort 4

	n	%¹	95% CI of the proportion
ECOG			
0			
1			
2			
3			
4			
UNK			

¹ Calculated percentage from the total of patients with available data

Table 70 Tumor characteristics overall in cohort 4

